#### **Primary outcome:**

Wilcoxon-Mann-Whitney test will be used to formally compare categorical outcome of glottis visualization (Cormack and Lehane classification) at the 5% significance level

between the two study groups; this test accounts for the ordinal nature of the outcome. If adjustment for imbalanced baseline covariates is required, we will attempt a proportion odds logistic regression model to compare randomized groups, reporting an odds ratio indicating the estimated odds of being better using videolaryngoscopy versus direct.

**Commented [WP1]:** See [here](#) for details on implementation and diagnostics.

If the proportional odds assumption does not hold after testing and also visualizing with further modeling, the outcome will be assessed using either an adjacent logit analysis or by combining categories and using chi-square test or binary logistic regression, as appropriate. The distribution of patients in each glottis visualization class will be reported for each randomized group.

**Commented [WP2]:** In `vgam` R package, the `acat()` function.

**Commented [WP3R2]:** Response MUST be an ordered factor. Returns an object of class vglmff to be used by vgam/vglm

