## Protocol

In the preoperative period, airway details for participating patients will be recorded by a research coordinator or anesthesia provider. Patients will be positioned supine and in a standardized ramped position on the OR table. Patients will be pre-medicated with midazolam, as clinically appropriate. All patients will be pre-oxygenated until the fraction of expired oxygen exceeds 80%.

Rapid sequence induction will be induced as preferred by the attending anesthesiologist, usually with a combination of lidocaine 1 mg/kg, propofol 2-5 mg/kg, fentanyl 1-3 µg/kg, and succinylcholine 1.5 mg/kg or rocuronium 1.0 mg/kg. Complete muscle relaxation will be confirmed by absence of palpable twitches in response to supra-maximal train-of-four stimulation of the ulnar nerve at the wrist.

Patients will be randomized 1:1 before induction, stratified for primary anesthesia providers (*experienced* – specialist, attending vs. *unexperienced* – trainees) to:

- Direct laryngoscopy using an appropriately sized Macintosh blade (usually size 3 or 4);
- McGrath videolaryngoscope in an appropriate size (usually blade size 3 or 4).

Randomization will be based on computer-generated codes accessed from the Redcap system.

Intubations will be performed with a regular endotracheal tube of adequate diameter, usually 7.0 mm to 8.0 mm. Endotracheal tubes will be equipped with a hockey-stick-shaped stylette, which will be prepared by the anesthesiologist in advance. The McGrath or the Macintosh blade will be introduced into oral cavity according to manufacturer recommendations and clinical practice. Minor airway manipulation procedures including BURP or Sellick maneuvers will be allowed to improve

visualization of the vocal cords. If initial intubation attempts fail, the endotracheal tube will be removed. Minor adjustments of patient's position and/or tube stylette will be used as clinically appropriate. Up to two intubation attempts will be made as necessary. Further airway management will follow clinical assessment of the anesthesiologist. The anesthesiologist will be permitted to terminate study participation and switch to an alternative method.

Once intubation is achieved, the endotracheal tube will be connected to the anesthesia circuit, and the endotracheal cuff pressure will be measured placed between 25 and 30 cm H2O.

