#### **Data analysis:**

##### **Statistical Analysis**

We will assess the balance of two randomized groups (McGrath videolaryngoscopy vs. direct laryngoscopy) on **baseline and demographic characteristics** using the absolute standardized difference (ASD), defined as the absolute difference in means, mean ranks, or proportions divided by the pooled standard deviation. Any characteristics with  $ASD > \text{maximum of } 0.10 \text{ and } 1.96 \sqrt{\frac{(n_1 n_2)}{n_1 + n_2}}$  will be considered imbalanced and will be adjusted for in the primary and secondary analyses.

**Formatted:** Font: Bold

All primary and secondary analyses will be completed using the modified intent-to-treat principle, thus including all randomized patients in whom intubation was attempted in the analyses. We will conservatively assign all missing outcome values as the highest possible score in the control group (direct laryngoscopy) and the lowest possible score in the treatment group (McGrath videolaryngoscopy) for all primary and secondary analyses.

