#### **Secondary outcomes:**

Randomized groups will be compared on the secondary outcome of Intubation failure (yes/no) via chi-square test and the associations reported using relative risk [97.5% confidence interval (CI)]. Randomized groups will be compared on the count of number of intubation attempts using either Wilcoxon-Mann-Whitney test or negative binomial regression, as appropriate. A Bonferroni correction will be applied and a significance criterion of  $0.05/2=0.025$  to control the overall Type I error at 5% level for two secondary hypotheses.

The exploratory and safety outcomes will be reported by study groups without formal statistical testing of the difference.

**Formatted:** Highlight

**Interim analyses** to assess efficacy and futility will be conducted at each 25% of the maximum planned enrollment. We will use a gamma spending function with gamma parameter= -4 for efficacy and -1 for futility.

**Sample size considerations.** **Sample size** is based on the primary outcome of glottis visualization (Cormack and Lehane classification) and the Wilcoxon-Mann-Whitney test. From the literature we assume a distribution of scores for the Direct Laryngoscopy group such that the proportion of patients in categories 1, 2a, 2b, 3 and 4 are 0.50, 0.30, 0.15, 0.04, 0.01, and that for the videolaryngoscopy the proportions are improved to 0.65, 0.25, 0.07, 0.02, 0.01. **We would thus need a total of 384 patients** to detect this difference or larger with 90% power at the 0.05 significance level. Incorporating a maximum of 3 interim analyses and a final analysis with the above-detailed spending functions will require a maximum **of N=438 patients**. Simulations indicate that if the specified difference is a good estimate of the true effect, the expected sample size is about 78% of the maximum sample size, or N=342. **In such a case**, the study will have a very good chance of crossing an efficacy boundary at interim looks 2 or 3.

Formatted: Font color: Red

Formatted: Font color: Red

Formatted: Font color: Light Blue

Because our estimates of laryngeal view are uncertain, **we plan to enroll a maximum of 800 patients in case the treatment effect is somewhat less than anticipated.**

Formatted: Font color: Red

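### Randomization is stratified by provider experience, but no planned primary or secondary test uses that stratum, and the default primary analysis names no summary effect with a confidence interval

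*Combined protocol and SAP*

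**What the plan says.** All references are to the combined protocol and SAP.

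- **Randomization (Protocol section):** "Patients will be randomized 1:1 before induction, stratified for primary anesthesia providers", in two groups: specialists and attendings versus trainees.
- **Primary test (Primary outcome, under Data analysis):** "Wilcoxon-Mann-Whitney test will be used to formally compare categorical outcome of glottis visualization (Cormack and Lehane classification) at the 5% significance level". No stratum is named.
- **Primary effect:** the only description promised in every case is this: "The distribution of patients in each glottis visualization class will be reported for each randomized group". An odds ratio appears only on a conditional path: "If adjustment for imbalanced baseline covariates is required, we will attempt a proportion odds logistic regression model to compare randomized groups". No CI is named there, and the fallback analyses name no measure.
- **Secondary outcomes:** failure gets a chi-square test and a relative risk with a 97.5% CI. For attempts, "Randomized groups will be compared on the count of number of intubation attempts using either Wilcoxon-Mann-Whitney test or negative binomial regression, as appropriate". Neither names the stratum.
- **Imbalance rule (Statistical Analysis):** characteristics above a standardized-difference cut-off "will be considered imbalanced and will be adjusted for in the primary and secondary analyses". The Measurements list has demographics, BMI, ASA status and airway findings. It does not include provider experience.
- **Interim looks:** analyses "to assess efficacy and futility will be conducted at each 25% of the maximum planned enrollment", with gamma spending of -4 for efficacy and -1 for futility. The sample-size text expects a good chance of an efficacy stop at look 2 or 3.

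**The concern.** Trainees and specialists probably obtain different laryngeal views, which is presumably why the randomization is stratified. A test that pools over a prognostic stratification factor leaves that variation in the noise and gives up some power that the design has already paid for.

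The second gap concerns reporting. A rank test gives a p-value but not the size of the effect. The primary outcome is less fully specified here than the secondary outcome of failure. The measure, its CI and any allowance for early stopping would be chosen after the data are seen. Because the plan expects to stop early, an effect taken straight from the class table tends to be too large in the trials that do so.

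**Working it through.** **1. The plan's own sample size.** With the stated proportions (direct 0.50, 0.30, 0.15, 0.04, 0.01; video 0.65, 0.25, 0.07, 0.02, 0.01), the probability of a better view with video, counting ties as half, is

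θ = (0.65×0.50 + 0.25×0.20 + 0.07×0.05 + 0.02×0.01) + ½(0.325 + 0.075 + 0.0105 + 0.0008 + 0.0001) = 0.3787 + 0.2057 = 0.584.

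The tie-corrected Noether formula is N = (z₀.₀₂₅ + z₀.₁₀)²(1 − Σp̄³) / [3(θ − ½)²], where p̄ is the mean class proportion over the two arms. This gives 10.507 × 0.7877 / (3 × 0.0844²) = 387. Using the null variance for the critical value and the alternative variance for power gives 382. Simulated power at 384 is 90.1%. The stated 384 therefore reproduces, and it rests on the pooled test. Four looks with the stated spending functions and non-binding futility inflate N by 1.136, and 384 × 1.136 = 436 against the stated 438. Binding futility gives 420.

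**2. Can the imbalance rule bring experience in?** The printed cut-off is 1.96√[n₁n₂/(n₁+n₂)].

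| Per arm | As printed | Fraction inverted |
|---|---|---|
| 192 | 19.2 | 0.200 |
| 219 | 20.5 | 0.187 |
| 400 | 27.7 | 0.139 |

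No plausible standardized difference reaches 19. Inverting the fraction would not help either, because experience is not on the list and stratified allocation should keep it balanced.

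**3. Power lost by pooling.** The documents give neither the stratum sizes nor the effect of experience, so both are assumed: equal strata, a cumulative odds ratio between provider groups of 2, 3 or 4, and the plan's marginal distributions kept. The van Elteren statistic is Σ(W_s − E W_s)/(n_s+1), divided by √[Σ Var_s/(n_s+1)²]. Group-sequential power at a maximum of 438 (at least 40,000 simulated trials per setting):

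| Provider odds ratio | Balanced: pooled / stratified | Not blocked: pooled / stratified |
|---|---|---|
| 2 | 90.9 / 91.4% | 90.2 / 91.1% |
| 3 | 91.6 / 92.7% | 90.3 / 92.3% |
| 4 | 92.0 / 93.8% | 90.4 / 93.7% |

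- The loss is 0.5 to 1.8 points with balance within strata and 0.9 to 3.3 points without blocking.
- With strata of 20/80 or 80/20, the loss is 0.2 to 1.2 points.
- If experience has no effect, power is 90.3% either way.
- At a maximum of 800, every power is at least 98.5% and the loss is at most about 0.5 points.
- With balance within strata, the fixed-sample two-sided size of the pooled test is 4.7, 4.0 and 3.7% at odds ratios 2, 3 and 4, so it is conservative.

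**4. Estimation after the looks.** The efficacy boundaries are Z = 3.155, 2.818, 2.439, 2.014 and the futility boundaries are −0.408, 0.527, 1.301. Futility stops are followed, and experience has no effect. The half-effect setting puts the video distribution midway between the two stated ones, so θ = 0.542.

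| Maximum, true θ | Early efficacy stop | Mean class-table θ in those | Ordinary 95% CI coverage, all trials | Coverage after early efficacy stop |
|---|---|---|---|---|
| 438, 0.584 | about 71% | 0.608 | about 91% | 94% |
| 800, 0.584 | 95% | 0.595 | about 95% | 97% |
| 438, 0.542 | 17% | 0.595 | about 92% | 76% |
| 800, 0.542 | 33% | 0.573 | about 92% | 87% |

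A stage-wise 95% CI covers 95.0 to 95.6% in these settings. After early efficacy stops at 438 (plan effect) it is 0.134 wide against 0.125, and 0.134/0.125 = 1.07. The stage-wise median-unbiased estimate in those trials averages 0.604, against 0.608 naive and 0.584 true.

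**The case against.** An unstratified test after stratified randomization is common and valid. The larger power losses depend on assumed provider effects, and at a maximum of 800 almost nothing is lost. All of this stands. A reader might infer that pooling invalidates the test or that 384 is wrong. The documents support neither: the test errs on the conservative side, and 384 reproduces.

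A reader might also think that the imbalance rule would bring experience in whenever it was unbalanced. It would not, for the reasons in step 2 of the working.

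On the effect measure, anyone can compute one from the class table, so the gap is largely missing detail and changes neither the test nor the type I error. That also stands. It would be too strong to say that ordinary intervals fail in general. At the plan effect and a maximum of 800, coverage is about 95%. At 438 the shortfall does not arise in the trials stopped early for efficacy, where coverage is 94%. Nor does the stage-wise method cure the exaggeration after an early stop; it moves the average only from 0.608 to 0.604.

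Finally, the simulated design may not be exactly the sponsor's. Its expected N is about 300 against the stated 342, so early stopping may be somewhat rarer than shown.

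**Conclusion.** The point holds as a low-cost improvement, not as a flaw in validity. The plan randomizes within provider experience and then analyses without it in the primary test and both secondary analyses. The cost is about 0.5 to 2 power points at a maximum of 438 with balanced strata, up to about 3 without blocking, and close to nothing at 800 or if experience does not matter. These figures rest on assumed provider odds ratios of 2 to 4 and equal strata.

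The default primary analysis also lacks a named effect measure, a CI and any allowance for the looks. The allowance matters mainly if the true effect is smaller than planned or if the maximum is 438. The estimation figures assume non-binding futility, which the plan does not state. Both maxima are shown because the spending calculation uses 438 while enrolment may reach 800.

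**What to change.** 1. Make the primary test a van Elteren (stratified Wilcoxon) test by provider experience, with the same statistic at every look.
2. For failure, use a Mantel-Haenszel test and a stratified relative risk with the planned 97.5% CI. For attempts, use a stratified rank test. Negative binomial regression need not be ruled out.
3. Always report one named primary effect measure, for example the experience-stratified probability of a better view with ties counted as half. It needs no proportional-odds check. Give a 95% CI by stage-wise ordering, which reduces to the ordinary one if no interim look is done.
4. State the look at which the trial stopped, because some exaggeration after an early stop remains.

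The cost is SAP wording. The stratum is already recorded at randomization, and stratifying loses no power if experience is irrelevant (90.3% either way at 438). The CI is about 7% wider after an early efficacy stop at a maximum of 438.

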#### **Secondary outcomes:**

Randomized groups will be compared on the secondary outcome of Intubation failure (yes/no) via chi-square test and the associations reported using relative risk [97.5% confidence interval (CI)]. Randomized groups will be compared on the count of number of intubation attempts using either Wilcoxon-Mann-Whitney test or negative binomial regression, as appropriate. A Bonferroni correction will be applied and a significance criterion of  $0.05/2=0.025$  to control the overall Type I error at 5% level for two secondary hypotheses.

The exploratory and safety outcomes will be reported by study groups without formal statistical testing of the difference.

**Formatted:** Highlight

**Interim analyses** to assess efficacy and futility will be conducted at each 25% of the maximum planned enrollment. We will use a gamma spending function with gamma parameter= -4 for efficacy and -1 for futility.

**Sample size considerations.** **Sample size** is based on the primary outcome of glottis visualization (Cormack and Lehane classification) and the Wilcoxon-Mann-Whitney test. From the literature we assume a distribution of scores for the Direct Laryngoscopy group such that the proportion of patients in categories 1, 2a, 2b, 3 and 4 are 0.50, 0.30, 0.15, 0.04, 0.01, and that for the videolaryngoscopy the proportions are improved to 0.65, 0.25, 0.07, 0.02, 0.01. **We would thus need a total of 384 patients** to detect this difference or larger with 90% power at the 0.05 significance level. Incorporating a maximum of 3 interim analyses and a final analysis with the above-detailed spending functions will require a maximum **of N=438 patients**. Simulations indicate that if the specified difference is a good estimate of the true effect, the expected sample size is about 78% of the maximum sample size, or N=342. **In such a case**, the study will have a very good chance of crossing an efficacy boundary at interim looks 2 or 3.

Formatted: Font color: Red

Formatted: Font color: Red

Formatted: Font color: Light Blue

Because our estimates of laryngeal view are uncertain, **we plan to enroll a maximum of 800 patients in case the treatment effect is somewhat less than anticipated.**

Formatted: Font color: Red

**Pilot patients:** We will enroll 5-10 pilot patients prior to the start of the study at each study center to familiarize the study team with the protocol and identify any systematic issues that might result in protocol modifications. Pilot patients will be randomized either to McGrath videolaryngoscopy or direct laryngoscopy group in the same manner as it is planned for the study. Pilot patients will not be included in the statistical analysis.

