**Secondary Outcomes:**

- Intubation attempts, defined as introducing the endotracheal tube into oral cavity to perform endotracheal intubation (1, 2, 3, etc.)
- Intubation failure, defined as
  - Failure to intubate within 3 intubation attempts
  - Need to switch intubators or intubation device
  - Need to stop study per anesthesiologist's discretion

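### Negative binomial regression on raw intubation attempts, the only regression named for this outcome, gives standard errors that are too large because attempts start at 1 and vary less than their mean

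*Combined protocol and SAP*

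**What the plan says.** All references are to the combined protocol and SAP.

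- **Method.** Under Data analysis, Secondary outcomes, the number of attempts is compared "using either Wilcoxon-Mann-Whitney test or negative binomial regression, as appropriate". No rule for choosing is given, and no robust or quasi-likelihood variance is mentioned.
- **Outcome.** Under Outcomes, Secondary Outcomes: "Intubation attempts, defined as introducing the endotracheal tube into oral cavity to perform endotracheal intubation (1, 2, 3, etc". The listed values begin at 1.
- **Analysis set.** Statistical Analysis defines a modified intent-to-treat set, "including all randomized patients in whom intubation was attempted in the analyses", so a count of zero is essentially excluded.
- **Upper limit.** The Protocol section says "Up to two intubation attempts will be made as necessary". One component of intubation failure is "Failure to intubate within 3 intubation attempts".
- **Adjustment.** Statistical Analysis says that imbalanced baseline characteristics will be adjusted for in the secondary as well as the primary analyses. For the primary outcome, a proportional-odds model is named for that case. For attempts, the only regression named is negative binomial.
- **Alpha.** Each of the two secondary hypotheses is tested at 0.05/2 = 0.025.

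**The concern.** A negative binomial model describes a count that can be zero and whose variance is at least its mean. Attempts cannot be zero here. If most patients are intubated at the first attempt, the values cluster at 1, with a mean a little above 1 and a small variance. The dispersion estimate then goes to its boundary of zero, the model becomes Poisson, and the Poisson variance is itself several times too large.

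Fewer attempts is one of only two secondary hypotheses and carries half of the Bonferroni alpha. If the regression branch is used with its default standard errors, a real reduction in attempts could be reported with a very wide interval and no significance. Because the choice between the two methods is open, two analysts could reach very different conclusions from the same data. The adjustment rule can also push the analysis towards the weaker branch, since a plain Wilcoxon-Mann-Whitney test takes no covariates.

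**Working it through.** **The plan's own figure.** The plan gives no rate, mean, variance or power for attempts. Its only sample-size figure is for the primary outcome: "We would thus need a total of 384 patients". With the stated view distributions, P(video better) + half of ties = 0.5844, and the average category proportions are 0.575, 0.275, 0.11, 0.03 and 0.01, whose cubes sum to 0.2123. The tie-corrected Noether formula gives

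N = (1.960 + 1.282)² × (1 − 0.2123) / (3 × 0.0844²) ≈ 387,

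within 1% of 384. This does not bear on attempts. From the plan I use only 1:1 allocation, the two maximum sizes (438 and 800, so 219 and 400 per arm) and alpha 0.025, taken as two-sided because the sidedness is not stated.

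**Step 1: bounds that need no assumed rate.** On values from 1 to K with mean m, the variance is at most (m − 1)(K − m).

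- Variance/mean is therefore at most K + 1 − m − K/m, which is largest at m = √K, where it equals (√K − 1)².
- K = 2: (1.4142 − 1)² = 0.172.
- K = 3: (1.7321 − 1)² = 0.536.

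Both are below 1, so underdispersion is certain under either cap. Filling in missing values at the extremes of the scale does not change this, because those values lie in the same range.

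**Step 2: effect on the standard error.** In the Poisson limit the model variance of a log mean is 1/(n·m). The true variance is v/(n·m²). The standard error is therefore too large by √(m/v).

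- Cap 2: at least √(1/0.172) = 2.41.
- Cap 3: at least √(1/0.536) = 1.37.

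The bound holds in each arm and so for the comparison.

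**Step 3: range over assumed first-attempt success** (not in the document):

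| First-attempt success | Cap 2 | Cap 3, 80% of the rest at attempt 2 |
|---|---|---|
| 70% | 2.49 | 1.97 |
| 80% | 2.74 | 2.17 |
| 85% | 3.00 | 2.38 |
| 90% | 3.50 | 2.77 |
| 95% | 4.70 | 3.72 |

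With no cap and a constant success probability f at each attempt, the factor is √(f/(1 − f)): 1.53 at 70%, 2.00 at 80%, 3.00 at 90% and 4.36 at 95%.

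**Step 4: an illustration.** Assume 1/2/3 attempts in 85/12/3% with direct and 93/6/1% with video laryngoscopy.

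- Means: 1.18 and 1.08. Variances: 1.60 − 1.18² = 0.2076 and 1.26 − 1.08² = 0.0936. Log mean ratio: ln(1.08/1.18) = −0.0886.
- Model SE, 219 per arm: √(1/(219 × 1.18) + 1/(219 × 1.08)) = 0.0900.
- True SE: √(0.2076/(219 × 1.18²) + 0.0936/(219 × 1.08²)) = 0.0324. Ratio 2.78.
- The expected model z is 0.0886/0.0900 = 0.98 against a critical value of 2.24. Since z varies with SD 1/2.78 = 0.36, significance needs a deviation of (2.24 − 0.98)/0.36 = 3.5 SD, about 0.02%.
- With the true SE, z is 0.0886/0.0324 = 2.74, and power is Φ(2.74 − 2.24), about 69%.

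Simulation agrees:

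| | Rank test | Count model, model-based SE |
|---|---|---|
| Power, N=438 | 69% | 0.02% |
| Power, N=800 | 92% | 0.6% |
| Rejection under no difference | 2.5% | 0.0% |

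**Step 5: a fitted example.** In one simulated data set with 219 per arm, the negative binomial dispersion estimate was 0.000015, effectively zero. The Poisson standard error was 0.0892 and the robust one 0.0326, a ratio of 2.7.

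**The case against.** The strongest reply is that the plan does not commit to the negative binomial model. The rank test is named first, and an analyst who sees that the model does not fit can use it. That is fair for the unadjusted comparison, and a reader who inferred that the planned analysis of attempts is invalid as it stands would go too far. It does not cover the adjusted case, where the rank test cannot be used and no other regression is named for attempts.

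How often adjustment would arise is uncertain. As the imbalance threshold is printed, 1.96·√(n1·n2/(n1+n2)) is about 20.5 at 219 per arm and would almost never be exceeded. If the reciprocal under the root was meant, the threshold is 1.96·√(2/219) = 0.19. Across the 20 listed characteristics, treated as independent, at least one would exceed it in about 1 − 0.95²⁰ = 64% of trials.

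A second reply is that the fault lies in the scale and the default variance, not in the model family. This stands. In the illustration, attempts minus 1 has variance/mean of 0.2076/0.18 = 1.15 and 0.0936/0.08 = 1.17, which suits a negative binomial. Simulated power on that scale was 66% and 92% at the two sizes, and a robust standard error on raw attempts gave 69% and 93%. The plan specifies neither remedy.

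A reader might also infer one fixed inflation factor, or a risk of false positives. The document supports neither. It gives no first-attempt success rate, so only the bounds are firm, and the error runs in the conservative direction. Nor is power always near zero: with 80/15/5% against 90/8/2% at N=800 the count model reached just under 10%, against 97% for the rank test.

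**Conclusion.** The point holds for negative binomial regression fitted to raw attempts with model-based standard errors. Under either limit in the document the standard error is too large: by at least 2.4 times with two attempts and at least 1.37 times with three. Over assumed first-attempt success of 70-95% the factor is about 2.0-4.7 under those caps. The open-ended listing of attempts would allow higher counts. The bounds then no longer apply, but the constant-success model in the working still gives a factor of 2.0 or more at 80% success or higher.

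The consequence is an over-wide interval and the loss of most of the power for one of two secondary hypotheses. Type I error is not inflated, the rank test is unaffected, and the primary analysis is untouched. The power figures rest on assumed attempt distributions and on enrolment reaching 438 or 800. The change should be made, but the defect does not threaten the trial's main conclusion.

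**What to change.** 1. Name the Wilcoxon-Mann-Whitney test as the single unadjusted method for attempts.
2. Replace negative binomial regression on raw attempts with one prespecified model for use when adjustment is required. The natural choice is proportional-odds logistic regression on 1, 2, and 3 or more attempts, as already planned for the primary outcome. A count model on attempts minus 1, or one with robust standard errors, would also serve. If attempts are in fact limited to two, attempts minus 1 is binary with variance/mean below 1, so a robust standard error or a binary model is then safer.
3. Report the proportion intubated at first attempt by arm.
4. Reconcile the two-attempt limit in the Protocol section with the three-attempt failure definition under Secondary Outcomes, because together they set the range of this outcome.

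The statistical change costs a sentence or two and no extra data. There is a small downside: the ordinal model reports an odds ratio instead of a ratio of means, and it assumes proportional odds with few patients in the top category.

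### Holm's step-down procedure would hold the same 5% error across the two secondary tests and never reject less than the planned Bonferroni rule (a cheap improvement, not an error)

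*Combined protocol and SAP*

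**What the plan says.** The 'Secondary outcomes' paragraph of the statistical section names two tests. The first compares groups on the "secondary outcome of Intubation failure (yes/no) via chi-square test", reported as a relative risk with a 97.5% confidence interval. The second compares the "count of number of intubation attempts using either Wilcoxon-Mann-Whitney test or negative binomial regression, as appropriate". For multiplicity, "A Bonferroni correction will be applied" with a criterion of 0.05/2 = 0.025, and the stated aim is "to control the overall Type I error at 5% level for two secondary hypotheses".

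Three other places bear on the point:
- 'Objectives and Hypothesis' expects the McGrath device to reduce both attempts and failures, not just one of them.
- The list of secondary outcomes makes "Failure to intubate within 3 intubation attempts" one of the components of failure, so the two outcomes overlap by definition.
- 'Sample size considerations' is based on the primary outcome only. No power, event rate or correlation is given for either secondary outcome, and no step-down procedure is mentioned.

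**The concern.** Bonferroni holds both tests at 0.025 whatever the other test shows. Once one null hypothesis has been rejected, only one remains, and the 5% aim allows that one to be tested at the full 0.05. Holm's procedure uses this, needs no added assumption and enrols nobody extra.

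What is at stake is narrow. The hypothesis in the objectives covers both outcomes. A trial in which one secondary p-value is below 0.025 and the other lies between 0.025 and 0.05 would support only one claim under the current wording, and both under Holm. The primary analysis, the sample size and every stated figure are unaffected.

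**Working it through.** **Inputs from the documents.** Family-wise error 0.05; two secondary tests; criterion 0.025 each; 97.5% interval for the failure relative risk.

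**Assumed, because the documents do not give them.** Two-sided tests; approximately normal test statistics with correlation ρ from 0 to 0.8 (to 0.9 for the error check); power per outcome at 0.025 of 80%, 60% or 15%.

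**1. The plan's own figure.** 0.05/2 = 0.025, exactly as stated. Under independence with both nulls true, the family-wise error is 1 − 0.975² = 0.0494, within 5%. The matching interval level is 1 − 0.025 = 97.5%, also as stated.

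**2. Error control under Holm.** The first step (smaller p-value ≤ 0.025) is the Bonferroni rule itself. With both nulls true, the two procedures therefore have the same family-wise error. Simulation with 1,000,000 pairs per setting gives 0.049 at ρ = 0, 0.047 at ρ = 0.5 and 0.036 at ρ = 0.9 for each. With one null true and the other test at 80% power, the false-rejection rate is about 0.025 under Bonferroni and 0.038 to 0.045 under Holm, still below 0.05.

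**3. Power for at least one claim.** Unchanged, for the same reason: 96.0% at ρ = 0 and 91.3% at ρ = 0.5 under either procedure, with 80% power per outcome.

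**4. Power for both claims, closed form at ρ = 0.** Let b be the power of a test at 0.025 and h its power at 0.05. Bonferroni supports both with probability b². Holm needs both p-values ≤ 0.05 and at least one ≤ 0.025, so the probability is h² − (h − b)².
- b = 0.80: the mean shift is 2.2414 + 0.8416 = 3.0830, so h = Φ(3.0830 − 1.9600) = 0.8693. Bonferroni gives 0.640; Holm gives 0.7557 − 0.0048 = 0.751. Gain 11.1 points.
- b = 0.60: the mean shift is 2.2414 + 0.2533 = 2.4947, so h = Φ(0.5347) = 0.7036. Bonferroni gives 0.360; Holm gives 0.4951 − 0.0107 = 0.484. Gain 12.4 points.

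**5. Power for both claims with correlation (simulation).** Entries are Bonferroni → Holm in percent, with the gain in points from unrounded values.

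| Power at 0.025 | ρ = 0 | ρ = 0.3 | ρ = 0.6 | ρ = 0.8 |
|---|---|---|---|---|
| 80% and 80% | 64.0 → 75.1 (11.1) | 66.6 → 76.5 (9.9) | 69.9 → 78.6 (8.7) | 72.9 → 80.4 (7.5) |
| 60% and 60% | 36.0 → 48.4 (12.4) | 40.6 → 52.1 (11.5) | 45.7 → 56.2 (10.5) | 50.1 → 59.6 (9.5) |
| 60% and 15% | 9.0 → 15.1 (6.1) | 11.5 → 18.0 (6.5) | 13.7 → 20.6 (6.9) | 14.7 → 21.9 (7.2) |
| 15% and 15% | 2.2 → 4.5 (2.3) | 4.1 → 7.3 (3.1) | 6.7 → 10.6 (4.0) | 9.1 → 13.5 (4.4) |

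At 80% each, power per outcome rises from 80% to between 83.7% (ρ = 0.8) and 85.5% (ρ = 0).

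**6. Why low power is in the range.** As an illustration only, suppose failure occurred as often as grades 3 and 4 in the sample-size assumptions: 0.04 + 0.01 = 5% with direct laryngoscopy and 0.02 + 0.01 = 3% with video. Take the stated maxima of 438 and 800 patients, allocated 1:1. Power at 0.025 is Φ[(0.02 − 2.2414·√(2·0.04·0.96/n)) / √((0.05·0.95 + 0.03·0.97)/n)].
- n = 219 per arm: Φ[(0.02 − 0.0420)/0.0187] ≈ 12%.
- n = 400 per arm: Φ[(0.02 − 0.0311)/0.0138] ≈ 21%.

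The plan does not define failure by grade, so these are not estimates of its power. They show that 60-80% cannot be taken for granted.

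**The case against.** The strongest reply is that nothing here is wrong. Bonferroni is prespecified, its arithmetic is correct and it achieves its stated aim at any correlation. This stands. A reader might infer from the overlap between attempts and failure that Bonferroni is invalid for correlated outcomes. It is not: correlation only makes it somewhat conservative (0.036 rather than 0.049 at ρ = 0.9).

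The second reply is that Bonferroni buys something. The 97.5% interval for the failure relative risk pairs directly with a 0.025 test, and Holm has no equally simple matching simultaneous interval. This also stands, so it would be too strong to say that the plan gives up power for nothing. It limits the case rather than ending it: the plan states an interval only for failure and none for attempts, and the interval can be kept with a note. Holm's false-rejection rate with one null true is also higher, though still within the 5% that the plan sets.

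A third reply is that Holm does not exploit correlation. Correct. Its gain exists at ρ = 0, and at 60-80% power per outcome it shrinks as correlation rises. The overlap of the two outcomes is therefore not the reason to switch.

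**Conclusion.** Cheap improvement, not an error in the plan. Holm meets the plan's stated 5% aim under any dependence, never rejects fewer hypotheses, and raises only the chance of supporting both secondary claims. With correlation 0 to 0.8, that rise is about 7 to 12 points if each outcome has 60-80% power at 0.025, and about 2 to 7 points if one or both have about 15%. All of these power and correlation values are assumed. A reader might take the larger range as the expected benefit in this trial, but the documents give no secondary power, so they do not support that. No stated figure, sample size or primary conclusion changes.

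**What to change.** Before any unblinded data are seen, replace the Bonferroni sentence with wording such as: the two secondary p-values will be tested by Holm's procedure at an overall 5% level; the smaller is compared with 0.025 and, only if it is significant, the larger is compared with 0.05. Keep the 97.5% interval for the failure relative risk as a conservative report, and add that it may include 1 when failure is the outcome tested at 0.05 and Holm rejects.

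The cost is one sentence of SAP text plus that note. No patients, data or primary analysis are affected. If the sponsor prefers test and interval always to agree, Bonferroni can stay, with that reason given in the plan.
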